Participants are considered active in the study for six months, from the time that they enroll in the program to the completion of the six-month post-enrollment follow-up survey.

The target analytic sample size for the impact study is 768 participants, with study groups being equal in size, for a target of 384 in-person participants and 384 on-demand participants.

Participant eligibility criteria. Individuals are eligible to participate in the program if they are incarcerated adults aged 18 years or older and within nine months of release from prison. All program enrollees who are receiving services at a site that has been authorized by the Ohio Department of Rehabilitation and Corrections (ODRC) to use tablets (and so can offer both delivery formats) for this program are eligible for the impact evaluation after giving informed consent to be randomly assigned to a study group. Approvals are for a specific tablet that the state of Ohio has granted a contract to provide technology services and devices into prisons across the state. Each warden (head of the specific institution) must approve the program delivered via tablet in their specific institution. This design allows for more equal opportunity for participants to be assigned to either delivery format. It also puts less burden on The RIDGE Project to meet enrollment numbers at numerous locations in order to get a sufficient sample to randomize. Program participants who have other commitments that prevent them from being able to participate in the in-person workshops are not eligible for random assignment; these participants are still offered TYRO Couples programming, but they are not part of the impact study sample. This within-facility design offers The RIDGE Project the opportunity to serve those in need without ever having to deny eligible applicants. In instances where unexpected situations arise, such as technological issues with the tablets, participants can opt out of the treatment group and receive in person services if it is more convenient or preferable to them. This would remove the participant from the study, but still allow the participant to continue with the TYRO curriculum. Having sites offer both delivery formats is invaluable for program delivery.

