Consent Process. Project staff follow a protocol that was approved by Solutions IRB, Inc. to solicit informed consent. Because the planned evaluation involves human subjects, The RIDGE Project understands program implementation requires both IRB approval and participant informed consent. Midwest Evaluation and Research (MER) has an established relationship with Solutions IRB, having secured more than 20 IRB approvals and renewals for evaluations it has conducted during the past five years. The original study and data collection plans for TYRO Couples were initially approved by Solutions IRB on 3/31/2021 and have been annually reviewed and approved three times on 3/15/2022, 3/4/2023, and 3/2/2024. IRB approval for TYRO Couples was recently renewed and will be renewed again in March 2025. Additionally, revisions to the study and/or data collection plan were submitted to the IRB as amendments and were approved on 4/15/2022, 2/23/2022, and 8/23/2023.

Informed consent procedures take place before random assignment and are the same for all study participants, regardless of ultimate study group assignment. To secure informed consent, after participants attend an orientation/enrollment session (in-person), the data manager, case manager, or facilitator describes the impact evaluation process and the risks and benefits of study participation. Individuals are then provided with a paper consent form that reiterates what program staff have explained about the study and provides contact information for the evaluation team or Solutions IRB, should they have any questions. Individuals indicate consent or refusal to participate in the study by signing the paper consent form, which is scanned and uploaded to MER's secure Dropbox by RIDGE program staff for the

evaluation team to keep in their records.

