The unit of randomization for this study is the individual. Participants are randomly assigned to a study group using the last single digit of their inmate number, a six-digit identifier assigned by the facility based on an inmate's chronological intake order. Because it is assigned by the facility, program staff and researchers have no influence in deciding who ends up in each study group, leaving it completely at random. With this method, half of the inmate population bears an even number, and the other half bears an odd number. The inmate number remains with the participant, which can also be used to look up their incarceration status within the ODRC facilities. Within a given cohort, participants with an odd last digit will be assigned to one study group, while participants with an even last digit will be assigned to the other study group. The intended probability of assignment to either study group is 50-50.

Which study group aligns with even/odd numbers varies randomly by cohort (e.g., odd numbers may be assigned to the on-demand format in one cohort but to the in-person format in the next cohort). Cohorts are formed around the length of time it takes to complete the program on a rolling basis based on demand. Evaluation staff use a random number generator in Excel to randomly vary what even or odd last digits mean for each upcoming cohort. The Excel spreadsheet with the results of the random number generator is shared with the RIDGE data manager via a secure Dropbox link. The data manager then prepares a sealed envelope with the random assignment information needed for each cohort's orientation, to be opened by the facilitator at the end of the orientation sessions when consent has been obtained. The facilitator then informs participants which group they have been assigned to based on the last digit of their inmate number. Once participants have been informed of their group assignment, they are considered part of the RCT study sample. The data manager enters study group assignments into the nFORM system. This process repeats with each new cohort in the RCT.

2. Data collection

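### Allocation is not concealed from one role that may explain the study for consent: the RIDGE data manager holds each cohort's odd/even key before orientation

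*Combined protocol and SAP*

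**What the plan says.** Section C.1, Random Assignment Process, assigns people within a cohort by whether the last digit of the inmate number is odd or even: all odd digits go to one group and all even digits to the second. The random element is one draw per cohort: "Evaluation staff use a random number generator in Excel to randomly vary what even or odd last digits mean for each upcoming cohort". That result then leaves the evaluator: "The Excel spreadsheet with the results of the random number generator is shared with the RIDGE data manager via a secure Dropbox link". What happens to it next is stated as follows: "The data manager then prepares a sealed envelope with the random assignment information needed". The envelope is made up for the orientation of each cohort, and its timing is fixed for one role; it is "to be opened by the facilitator at the end of the orientation sessions when consent has been obtained". The same section argues that, because the facility issues the inmate number, neither program staff nor researchers can affect group membership.

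Section C.1, Consent Process, says who conducts the discussion before people sign: "the data manager, case manager, or facilitator describes the impact evaluation process and the risks and benefits of study participation". Each individual then records consent or refusal on a paper form.

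Section C.1, Participant eligibility criteria, adds an exclusion that applies before assignment: "Program participants who have other commitments that prevent them from being able to participate in the in-person workshops are not eligible for random assignment". It does not say who makes that judgement, or at what point.

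**The concern.** Random assignment protects against selection only if those who influence entry cannot foresee the next assignment. Here a single bit of information per cohort, combined with a number already on each person's record, gives every assignment in that cohort. A person who holds that bit and also presents the study could, knowingly or not, present it differently according to the arm a candidate would receive.

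Selection at this stage would also sit outside most of the plan's monitoring. Section C.1 counts people as part of the trial sample only once they have been told their group, so anyone who declines or is excluded earlier does not enter the attrition assessment in Section D.2. What is at stake is the comparability of the two groups at entry, on which the impact estimates for both primary outcomes rest.

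**Working it through.** The plan states no figure on this point, so the main check is to trace who knows what, and when.

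1. **Key created.** Evaluation staff generate it for each upcoming cohort (Random Assignment Process).
2. **Key passed on.** The RIDGE data manager receives the spreadsheet and makes up the envelope for that cohort's orientation. The key is therefore known to this role before the envelope is sealed, and so before consent.
3. **Consent discussion.** It is held by the data manager, the case manager or the facilitator (Consent Process).
4. **Envelope opened.** The facilitator opens it after consent.

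| Role | May explain the study | Has the key before consent |
|---|---|---|
| Data manager | Yes | Yes |
| Case manager | Yes | Not stated |
| Facilitator | Yes | No (sealed envelope) |

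The gap is in the first row only. No sentence bars the data manager from explaining the study to a cohort whose key he or she has handled.

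**Do the interim counts help?** Figure A.3 lists 206 and 190 participants eligible for follow-up.
- n = 206 + 190 = 396; 206/396 = 52.0%.
- The exact two-sided binomial test against 50-50 gives p = 0.45. The normal approximation is z = (206 − 190)/√396 = 0.80, p = 0.42.
- These are follow-up-eligible counts, not everyone randomised.
- Suppose 10% of the people bound for one arm were lost before assignment. The expected split would be 0.9/1.9 = 47.4% to 52.6%, a shift of 2.6 percentage points. The standard error at n = 396 is 0.5/√396 = 2.5 points, so a shift of that size would usually go unnoticed.
- Selection by type of person, in both arms, need not move the totals at all.

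The counts neither support nor refute the point.

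**Scale, by assumption only.** Let q be the share of one arm's candidates steered out, and D their difference in prognosis in SD units. Neither figure is in the documents. Take q = 0.02 to 0.10 and D = 0.3 to 0.5.
- If D compares those removed with those who remain, bias = q × D: 0.02 × 0.3 = 0.006 to 0.10 × 0.5 = 0.050 SD.
- If D compares those removed with the whole group, bias = q/(1 − q) × D: (0.02/0.98) × 0.3 = 0.006 to (0.10/0.90) × 0.5 = 0.056 SD.
- For comparison, with 384 per group, an assumed two-sided 5% level and 80% power, the detectable unadjusted difference is (1.960 + 0.842) × √(2/384) = 0.20 SD.

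These biases are for an unadjusted contrast. The planned model adjusts for baseline score and demographics, so only the part of prognosis that those covariates miss would remain.

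**The case against.** The strongest reply is that the plan already conceals the key where it matters most. The facilitator, who runs the sessions, sees nothing until consent is complete; the case manager is not said to receive the key; and the consent text says *or*, so the data manager may never have explained the study to any cohort. Participants sign for themselves. Section D.2 checks baseline differences on demographics and outcomes, Section D.3 adjusts for baseline score, age, gender and race, and the evaluator keeps its own record of who should be in which group.

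Most of this stands, and it limits the point to one role. It does not close the gap. Baseline checks and adjustment deal with measured characteristics only. The evaluator's record is meant to detect crossover after assignment, not selection before it. Issuing the inmate number at the facility stops staff from altering a number, but not from knowing what it implies.

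A reader might infer more than this, and the documents do not support it:
- *That allocation is open to enrolling staff in general.* It is shown for the data manager only.
- *That the data manager applies, or is present for, the exclusion for other commitments.* The plan does not say who applies it. It is a possible route and no more.
- *That selection took place.* Nothing in the documents shows this, and the counts cannot.

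**Conclusion.** The point holds for one role. As written, the plan lets the RIDGE data manager know each candidate's arm before consent and also take part in the consent discussion. This rests on two readings: that preparing an envelope for orientation means having the key before it, and that no unwritten rule keeps the data manager out of consent. If the data manager never explained the study or judged eligibility, a statement to that effect would settle the matter.

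The size of any bias is unknown. The illustrative range is small beside the detectable difference, so this is an inexpensive improvement to make and a fact to disclose. It is not a reason to distrust the trial.

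**What to change.** **Remaining cohorts** (Wave 1 runs to November 30, 2024; the plan is dated August 22, 2024). Add one of these to Section C.1:
- Whoever holds the key takes no part in consent or eligibility decisions; the case manager or facilitator explains the study. This is the simpler option and needs no new staff.
- The evaluator keeps the key and releases it only after the list of consented participants for that cohort is fixed. Signed forms already go to the evaluator through its Dropbox, but technology limits inside the facilities may mean a wait.

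**Cohorts already enrolled.** Report whether the data manager took part in consent. Where refusers' inmate numbers are recorded, compare refusals by intended arm (last-digit parity combined with the cohort's key). Do the same for exclusions due to other commitments only if these were logged. If the records do not exist, say that this cannot be checked.

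**Reconcile at the same time.** Table 5 places the baseline surveys after randomisation, whereas the Random Assignment Process places them before it. The order decides whether a refusal recorded on the baseline survey comes before or after assignment.

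**Cost.** One sentence in the plan, a small change in who explains the study or a short wait for the key, and one tabulation from records where they exist. With about 100 days of enrolment left and a six-week program (100/42 ≈ 2.4 cycles), much of the value lies in the disclosure and the refusal comparison.

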Consent or refusal can also be indicated through the local evaluation baseline survey. The first item on the evaluation baseline survey reads: "By answering this question and typing my name below, I am acknowledging that I have been presented information about this study and am providing my voluntary consent to participate in the study described. I also understand that I can quit participating at any time and can skip any questions in this survey that I do not wish to answer without consequence, and further, I understand that all my answers are confidential and will not be shared with anyone outside of the research team." This item assures that the study information has been presented to participants and they know their rights as human subjects in a research study. Should someone decide that they no longer want to participate in the study, they can indicate on the local evaluation baseline survey and refuse to participate any further in the evaluation.

Random Assignment Process

After informed consent has been obtained, random assignment occurs. Random assignment takes place after one or two in-person orientation sessions, giving participants time to complete enrollment paperwork, provide consent, and take baseline surveys. During the one or two-in person orientation sessions, no curriculum content is covered until participants begin either the in-person or on-demand delivery format. Participants are randomized into the in-person or on-demand delivery format prior to the class starting, typically in one to two weeks. The participants attend classes one and two and are told at the beginning of class two whether they will be taking the course in person or via tablet.

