To increase follow-up response rates and with the approval of OFA, alternative follow-up data collection procedures were developed by the RIDGE and evaluation teams for one service site that enrolls most of the impact study participants at about 78%, Franklin CBCF. Many impact study participants from the Franklin CBCF service site go on to participate in a Department of Labor initiative immediately following their release from prison. As part of this initiative, participants are bussed from the Franklin CBCF to an American Jobs Center. TYRO Couples RCT participants who are part of this initiative are invited to complete a paper follow-up survey on the Thursday prior to the bus taking participants to the American Jobs Center the following Monday morning. Eligible participants who completed the survey will be handed a physical \$50 gift card upon boarding the bus. This follows guidelines of prisons where no monetary incentives can be administered on the premises. To be eligible for the follow-up survey, participants must have a signed consent form on file and have taken either the nFORM entrance survey or the local evaluation baseline survey. Evaluation staff will coordinate with program staff to ensure only those who are eligible for the follow-up survey are offered it. Paper surveys will be sealed in an envelope where they are given to a team member certified in protecting human research participants to enter the surveys into Qualtrics. Paper surveys are to be kept in locked storage at RIDGE offices and will be stored for a minimum of three years before being destroyed in accordance with IRB guidelines. This process is set to begin in May 2024.

Table 5. Key features of the data collection

Study group	Data source	Timing of data collection	Mode of data collection	Party responsible for data collection	Start and end date of data collection
Intervention (on-demand)	Survey Wave 1 (nFORM baseline and local evaluation baseline surveys)	Immediately following informed consent and randomization during orientation (within 1-2 weeks of enrollment)	In-person paper survey	RIDGE Staff	April 11, 2023 – November 30, 2024
	Survey Wave 2 (nFORM exit and local evaluation post-surveys)	Six weeks after program enrollment	In-person paper survey	RIDGE Staff	May 23, 2023 (or February 2023 for pilot cohort) – January 11, 2025

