All outcome measures for this study are constructed averages calculated using a number of theoretically and empirically related survey items. As mentioned in the previous section, a respondent who answers some but not all survey items in a given outcome construct will have their outcome value assigned as missing if they do not respond to at least 80% of the items in the construct. We will not impute missing baseline or outcome data for our analyses. Based on the recommendation from ACF, we will use the cautious attrition threshold from the What Works Clearinghouse (WWC) to assess whether attrition can be considered high or low.

Assessment of baseline equivalence

Per the WWC's standards, we will use effect sizes (i.e., standardized mean differences), to examine the baseline equivalence between the study groups. Effect size is defined as the difference between the intervention group mean and the comparison group mean, divided by the pooled standard deviation. We will calculate the effect size for demographic characteristics (such as gender, age, and race/ethnicity, as reported on the nFORM Applicant Characteristics Survey) and each baseline outcome of interest depending on the type of variable: Hedge's g , for continuous variables; and Cox's index, for dichotomous variables. We can determine baseline equivalence by comparing each outcome's effect size using the WWC standard, which suggests that if the corresponding effect size is 0.05 or less in absolute value, it is considered "small," and we can conclude that it satisfies baseline equivalence without statistical adjustment. However, if the effect size falls between 0.05 and 0.25, it is considered "moderate," and it will require a statistical adjustment to meet baseline equivalence (we will use statistical adjustments such as regression adjustments or matching/weighting). Lastly, in the case that the effect size is greater than 0.25, it will be considered "large", which shows that the differences at baseline are too large to meet WWC standards, even with statistical adjustments. In that case, we will apply appropriate caveats to any interpretation of the results.

Condition crossover

At the primary RCT enrollment site, Franklin CBCF, condition crossover is not possible due to restrictions put in place when designing the implementation of the two delivery formats. If a participant who was

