Next, we will conduct an analysis to see how outcome construct measures change if we use mean imputation to replace missing items in the multi-item scales used to create our outcome variables. This is the mean based on observed values from the rest of the sample for that item. The current plan is not to use any imputation for outcome measures, including constructed outcomes from multiple survey items, and instead to make the denominator for the calculation of the average score be equal to the number of non-missing items in that construct.

Finally, we plan to conduct a sensitivity analysis regarding the timing of the follow-up survey. Given changes in follow-up data collection protocol at Franklin CBCF, we anticipate that some respondents will have taken their paper follow-up survey earlier than intended. The sensitivity analysis will repeat our analyses using only people who completed their follow-up survey within the intended data collection window (5-7 months post-enrollment).

5. Analyses addressing secondary research questions

The analytic approach for answering the secondary research question about partner relationship behaviors will be the same as the approach taken for the primary research questions.

Figure A.3. CONSORT diagram for individual clients, for studies in which consent occurred before assignment

Eligible for 6-month post-enrollment follow-up (n = 206)

To be eligible, a participant must have provided consent and taken either the nFORM baseline or local evaluation baseline survey

Completed follow-up (n = 64)

Data collection: July 1, 2023-July 22, 2024

Reasons for non-completes (n = 1) (that can be accounted for)

Consent revoked (n = ___), declined survey (n = ___), deceased (n = ___), dropped out (n = 7), moved (n = ___), incarcerated (n = 1)

Eligible for 6-month post-enrollment follow-up (n = 190)

To be eligible, a participant must have provided consent and taken either the nFORM baseline or local evaluation baseline survey

Completed follow-up (n = 52)

Data collection: July 1, 2023-July 22, 2024

Reasons for non-completes (n = 1) (that can be accounted for)

Consent revoked (n = ___), declined survey (n = ___), deceased (n = ___), dropped out (n = 4), moved (n = ___), incarcerated (n = 1)

Figure A.4. Survey items linked to research questions

Measure	Item Response	Are these items linked to a primary research question?	Are these items linked to a secondary research question?
Partner relationship beliefs 8 items			No

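### The RCT sample is defined from the moment participants are told their arm rather than from assignment, so people assigned but never told fall outside it and may go uncounted in attrition

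*Combined protocol and SAP*

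**What the plan says.** Section C.1 (Random Assignment Process) sets entry to the trial at notification: "Once participants have been informed of their group assignment, they are considered part of the RCT study sample". Assignment itself follows from the odd or even last digit of the inmate number and a key drawn at random for each cohort before its orientation.

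The plan describes the timing in three ways:

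- Early in the same part of Section C.1, consent and baseline surveys come first, followed by randomisation: "Participants are randomized into the in-person or on-demand delivery format prior to the class starting, typically in one to two weeks". Participants "are told at the beginning of class two whether they will be taking the course in person or via tablet".
- Later in that part, the key is in a sealed envelope "to be opened by the facilitator at the end of the orientation sessions when consent has been obtained". Next: "The facilitator then informs participants which group they have been assigned to based on the last digit of their inmate number".
- Table 5 (Section C.2) gives the timing of the baseline survey as "Immediately following informed consent and randomization during orientation", which puts the survey after randomisation.

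For follow-up, Figure A.3 applies another rule: "To be eligible, a participant must have provided consent and taken either the nFORM baseline or local evaluation baseline survey". Section C.2 states the same rule for the Franklin CBCF follow-up. On attrition, Section D.2 says "we will use the cautious attrition threshold from the What Works Clearinghouse (WWC) to assess whether attrition can be considered high or low". It does not say from which count attrition is measured.

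**The concern.** In a randomised comparison the sample should be fixed at assignment. A rule that starts the sample later excludes, by definition, anyone lost in between. Here entry depends on a step carried out by the facilitator, who has by then opened the key and who delivers only the in-person format.

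Most of what is at stake is the accounting. The analysis is complete-case, so a person who leaves early and never completes follow-up does not enter the model under either definition. That person does belong in the denominator of overall and differential attrition, which the plan will use to judge how far the comparison can be trusted. If the denominator starts at notification, those losses cannot be seen. If they differed by arm, the groups compared would no longer be the groups as randomised, and nothing in the report would show it.

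**Working it through.** **1. Is there an interval between assignment and notification?**

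- First account in Section C.1: randomised before the class starts, told at the start of class two. There is an interval.
- Second account in Section C.1: envelope opened at the end of orientation, participants then told. There is almost no interval for those present. A participant who consented at a first orientation session and is absent at the announcement still has an arm without having been told it.
- Table 5: gives no notification time, but reverses the order of baseline survey and randomisation.

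**2. How would the plan count a person who was assigned but never told?**

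| Rule | Consented, baseline survey taken | Consented, no baseline survey |
|---|---|---|
| Arm (digit and key) | determined | determined |
| RCT sample (Section C.1) | out | out |
| Follow-up eligibility (Figure A.3) | in | out |
| Attrition denominator (Section D.2) | not stated | not stated |

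The two stated definitions disagree in the first column, and neither counts the person in the second. The treatment indicator in Section D.3 is based on random assignment and is compatible with either definition.

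**3. How large could the effect be?**

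The plan gives no attrition figure to reproduce. The inputs are the two follow-up boxes in Figure A.3 (data pulled July 22, 2024): 64 of 206 and 52 of 190 completed. The readable text does not say which box is which arm.

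- Non-completion by box: 1 − 64/206 = 68.9%; 1 − 52/190 = 72.6%.
- Difference: 3.7 percentage points.
- Overall: 1 − 116/396 = 70.7%.

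Let f be the share of assigned people lost before being told and missing from these counts. The corrected denominator is N/(1 − f). The documents do not give f; 2%, 5% and 10% are assumptions.

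Equal loss in both arms:

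- f = 2%: 396/0.98 = 404.1; overall 1 − 116/404.1 = 71.3%; difference 3.6 points.
- f = 5%: 396/0.95 = 416.8; overall 72.2%; difference 3.5 points.
- f = 10%: 396/0.90 = 440; overall 73.6%; difference 3.3 points.

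Loss in one arm only:

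- From the group of 190: f = 5% gives 190/0.95 = 200 and 64/206 − 52/200 = 5.1 points; f = 10% gives 211.1 and 6.4 points.
- From the group of 206: f = 5% gives 216.8 and 64/216.8 − 52/190 = 2.1 points; f = 10% gives 228.9 and 0.6 points.

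Equal loss of 2-10% therefore raises the overall figure by about 0.6 to 2.9 points and barely moves the difference. Loss from one arm can move the difference in either direction.

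**The case against.** The strongest reply is that the second account in Section C.1 makes opening the envelope and telling participants consecutive steps, so hardly anyone can be lost between them; the interval comes mainly from the first account. That is fair, and it is why the passages must be reconciled. It does not cover a participant who is absent at the announcement.

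A reader might infer that these people are in fact dropped from the attrition count. The documents do not establish that. No denominator is stated, and the follow-up rule would keep a consented person with a baseline survey, so the 206 and 190 may already include them. The upper boxes of the CONSORT diagram are not in the readable text, so the number randomised may be shown there. This objection stands, and it makes the calculations illustrative.

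A reader might also infer selective loss by arm. People who have not been told their arm cannot react to it, so most such losses should be similar in both arms. The facilitator could act on the key, or an absentee could learn the odd/even rule from classmates and stay away, but no passage reports either. What remains is that neutrality is not assured and, under the present definition, would not be measured.

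Finally, the interim counts are not final attrition. Baseline collection runs to November 30, 2024 and follow-up to May 31, 2025, and the printed eligibility rule has no elapsed-time condition, so some of the 396 may not yet have been due.

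**Conclusion.** The concern holds as a matter of definition. The plan's only explicit statement of who is in the RCT sample excludes people who have consented and been assigned but not told, and it differs from the follow-up eligibility rule. Their omission from overall and differential attrition is possible but not shown.

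The size is unknown and probably small. The range above (72.2-73.6% overall under equal loss of 5-10%; a difference of 0.6 to 6.4 points under one-sided loss of up to 10%) rests on an assumed loss, on the further assumption that these people are missing from the 206 and 190, and on interim data. It does not show that the attrition class would change: the documents do not reproduce the threshold values, and interim non-completion is already about 71%. The change is worth making because it removes an exclusion after assignment and makes differential attrition auditable.

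**What to change.** Replace the sentence in Section C.1 with wording such as: *The RCT study sample is every participant who has consented when the cohort's envelope is opened, in the arm given by the last digit of the inmate number and that cohort's key, whether or not the participant has been told the arm.*

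Then:

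- use that count as the number randomised in the CONSORT diagram;
- state in Section D.2 that it is the denominator for overall and differential attrition;
- report, by arm, the number never told;
- reconcile the two accounts in Section C.1 and Table 5 on the order of baseline survey, assignment and notification.

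The cost is a rewritten sentence, these consistency edits and a recount. Section D.2 (Condition crossover) says the evaluation team has a record of each participant's intended group from the digit and the cohort schema, and Section C.1 has the signed consent forms sent to it. The recount should be feasible if those records extend to people never told, which the plan does not state. Past cohorts need not be contacted again for Wave 3. Stated attrition may look slightly less favourable.
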